5.2.5 Following the Procedure

Short tirofiban will be infused for the duration of the procedure plus a minimum of one hour and up to a maximum of two hours post-PCI. For example, if the procedure takes 25 minutes (i.e. 25 minutes from the time of advancement of the guidewire out of the guiding catheter to final removal of the guiding catheter) then tirofiban will be infused for a total of 25 minutes plus a minimum of one hour (for a total infusion time of 85 minutes) and up to a maximum of two hours (for a total infusion time of 145 minutes). For another example, if the PCI procedure takes 55 minutes, then tirofiban will be infused for a total of 55 minutes plus a minimum of one hour (for a total infusion time of 115 minutes) and up to a maximum of two hours (for a total infusion time of 175 minutes).

Eptifibatide will be infused for a total of 18 hours following PCI (minimum 12 hours mandated).

Long tirofiban was infused for a total of 18 hours following PCI (minimum 12 hours mandated).

During study drug administration and following discontinuation of study drug, the patient will be observed for signs of bleeding. Blood pressure and heart rate will be monitored according to the institution's standard procedures.

For the definition of procedure duration, final removal of the guiding catheter will define procedure completion.

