9.6 Planned Methods of Analysis

General Principles

For continuous variables, descriptive statistics (mean, SD, median, and quartiles) will be tabulated by treatment group. For categorical variables, the number and proportion of patients in each category will be tabulated.

The primary and secondary endpoints will be analyzed using the MITT population. Safety endpoints will be analyzed using the safety population. Demographics, baseline characteristics, and other study assessments will be analyzed using the MITT and intent-to-treat (ITT) population.

Confidence intervals will be used to assess hypotheses of non-inferiority and superiority. Details of the statistical methods will be developed in the Statistical Analysis Plan (SAP).

Demography and Baseline Characteristics

All appropriate background data will be summarized for each treatment group. If there are heterogeneities between two groups in any of the patient characteristics that are of clinical importance or could affect the study outcome, the impact of the imbalances will be investigated. If necessary, adjustments may be made in the efficacy and safety analysis and will be documented in the study report.

Primary Endpoint

The first primary and co-primary endpoints will be analyzed by the use of a one-sided 97.5% confidence interval

Subgroup/Covariate Analyses

Formal subgroup analyses will be performed by including the appropriate interaction terms in multivariable logistic regression models. The effects of potential covariates (see Section 9.3.4) will be assessed using multi-variable logistic regression.

Secondary Endpoints

The analysis of the secondary endpoints will be conducted in the same way as for the primary endpoint.

Safety Endpoints

The analysis of these safety endpoints will compare the incidence in the short tirofiban treatment group to the incidence in the eptifibatide group, the incidence in the short tirofiban treatment group to the incidence in the long tirofiban treatment group and the incidence in the long tirofiban treatment group to the incidence in the eptifibatide group, using the Fisher's mid-p (Berry and Armitage, 1995). Serious adverse events will also be tabulated overall and by severity for each treatment group.

Multiplicity (Multiple Endpoints)

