3.10 Analysis of the Study Endpoints

3.10.1 Analysis of the Primary Endpoint

To evaluate the effectiveness of tirofiban versus eptifibatide, we look at the proportion of patients with at least one of the following endpoint measurements: death, PPM, uTVR or REPLACE-2 Major bleeding within 48 hours following PCI or hospital discharge, whichever comes first. For each pairwise comparison:

- The short tirofiban group is non-inferior to the eptifibatide group;
- The short tirofiban group is non-inferior to the long tirofiban group;
- The long tirofiban group is non-inferior to the eptifibatide group;

The following hypothesis will be tested:

$$H_0: C - T \leq -0.191$$

$$H_1: C - T > -0.191$$

To test this hypothesis, the difference ($C - T$) and its associated one-sided 97.5% confidence interval will be calculated. If the lower bound of the interval is greater than -0.191, the non-inferiority will be claimed. In order to compute the risk (proportion) difference for data with binary

response (“Yes” vs. “No”), a bivariate logistic regression will be performed for each pairwise comparison with the following specifications:

- The dependent variable will be “composite endpoint” and the independent factor will be “treatment group”;
- The risk (proportion) difference between two methods as well as its confidence interval will be estimated;
- The non-inferiority margin is 19.1%

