3.10.4 Potential Covariates and/or Subgroups

As an exploratory analysis, appropriate univariate statistics will be used to identify potential confounders for inclusion in multivariable regression models for assessment of the primary endpoint. The following covariates will be considered:

- Patient with acute coronary syndromes (defined as any previous diagnosis of unstable angina, NSTEMI or STEMI)
- STEMI > 48 hours
- Stable angina
- Baseline troponin (positive vs. negative)
- Planned PCI access (femoral vs. radial)
- Number of stents implanted
- Number of vessels treated (multivessel vs. single vessel)
- Total infusion time
- Patients receiving P2Y12 antagonist therapy between 24 and 6 hours prior to randomization
- Patients receiving P2Y12 antagonist therapy between 6 and 1 hours prior to randomization
- Patients receiving P2Y12 antagonist therapy between 1 hour prior to randomization and 15 minutes after completion of the PCI procedure
- Type 2 diabetes mellitus
- Age < 65 years, ≥ 65-74 years and ≥ 75 years
- Sex
- Clopidogrel
- Prasugrel
- Ticagrelor
- Indication for PCI (Urgent vs. Elective)

RESPONSIVE
RELIABLE
RESULTS

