Note: This table will also be repeated for Per-Protocol Population.

Table 15 (a) Multivariate Logistic Regression Models for Primary Outcome – mITT Population

Parameter	Level	Estimate	Standard Error (SE)	Odds Ratio (OR)	95% CI for OR	Risk (Proportion Difference)	Standard Error (SE) of Risk Difference	95% CI for Risk Difference	p-value *
Primary composite outcome	Short Tirofiban vs. Eptifibatide								
Primary composite outcome	Short Tirofiban vs. Long Tirofiban								
Primary composite outcome	Long Tirofiban vs. Eptifibatide								

* p-value is the overall p-value from the logistic regression model.

Note: The following potential covariates, as well as all significant 2-way interaction terms, will be assessed using appropriate univariate statistics for consideration in the multivariate regression models:

- *Patient with acute coronary syndrome*
- *STEMI > 48 hours*
- *Stable angina*
- *Baseline troponin (positive vs. negative)*
- *Planned PCI access (femoral vs. radial)*
- *Number of stents implanted*
- *Number of vessels treated (multivessel vs. single vessel)*
- *Total infusion time*
- *Patients receiving P2Y12 antagonist therapy between 24 and 6 hours prior to randomization*
- *Patients receiving P2Y12 antagonist therapy between 6 and 1 hours prior to randomization*
- *Patients receiving P2Y12 antagonist therapy between 1 hour prior to randomization and 15 minutes after completion of the PCI procedure*
- *Type 2 diabetes mellitus*
- *Age < 65 years, ≥ 65- 74 years and ≥ 75 years*

- *Sex*
- *Clopidogrel*
- *Prasugrel*
- *Ticagrelor*
- *Indication for PCI (Urgent vs. Elective)*

Note: This table will also be repeated for Per-Protocol Population.

Table 16. Descriptive Statistics of Secondary Outcomes by Treatment Group – mITT Population

Parameter	Treatment Group		
	Short Tirofiban (N=)	Short Tirofiban (N=)	Short Tirofiban (N=)
Secondary outcome 1, n (%)			
Yes			
No			
Secondary outcome 2, n (%)			
Yes			
No			
Secondary outcome 3, n (%)			
Yes			
No			
Secondary outcome 4, n (%)			
Yes			
No			
Secondary outcome 5, n (%)			
Yes			
No			
Secondary outcome 6, n (%)			
Yes			
No			
Secondary outcome 7, n (%)			
Yes			
No			

Parameter	Treatment Group		
	Short Tirofiban (N=)	Short Tirofiban (N=)	Short Tirofiban (N=)
Secondary outcome 8, n (%)			
Yes			
No			

Note: The definitions of secondary outcomes are:

- *Secondary outcome 1: death, PPM or uTVR within 48 hours following PCI or hospital discharge, whichever comes first*

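### Total infusion time is fixed by the assigned arm and should not be a candidate confounder in the exploratory adjusted model; separately, the multivessel flag in Table 13 is miscoded

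*SAP*

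**What the plan says.** The confirmatory analysis contains treatment only. SAP 3.10.1 states that "a bivariate logistic regression will be performed for each pairwise comparison", with treatment group as the independent factor.

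SAP 3.10.4 then adds, as an exploratory step, that "appropriate univariate statistics will be used to identify potential confounders for inclusion in multivariable regression models for assessment of the primary endpoint". The list that follows includes "Total infusion time". The note to mock Table 15(a) repeats the list, says that its members "will be assessed using appropriate univariate statistics for consideration in the multivariate regression models", and adds significant two-way interactions. That table reports an adjusted risk difference with a 95% interval for all three comparisons and is repeated for the per-protocol population. Protocol 9.3.4 lists the same variable, and Protocol 9.6 says: "The effects of potential covariates (see Section 9.3.4) will be assessed using multi-variable logistic regression".

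Protocol 5.2.5 fixes the durations. Short tirofiban is "infused for the duration of the procedure plus a minimum of one hour and up to a maximum of two hours post-PCI". Eptifibatide and long tirofiban run for 18 hours after PCI, with at least 12 hours mandated.

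SAP mock Table 13, footnote 2, derives vessel involvement from the number of stents implanted and codes one or more stents as multivessel.

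**The concern.** A variable determined by randomised assignment cannot confound the effect of that assignment. The planned durations do not overlap between short tirofiban and either comparator, so infusion time nearly reproduces the arm indicator. Putting both in one model asks whether the arms differ at equal duration. In short versus long tirofiban, duration is the whole question. In short tirofiban versus eptifibatide it is one part, since the drugs also differ.

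The adjusted estimate would then rest on ordinary within-arm variation and on patients who departed from the planned duration. Those departures are not random. A persisting thrombotic complication extends the short infusion to at least 12 hours (Protocol 5.1 and 5.2.4). Protocol 5.2.4 and Appendix 3 give comparator patients with a complication no maximum duration, so their infusions can lengthen too. Uncontrolled bleeding stops the drug (Protocol 5.2.8) and mainly shortens the long infusions. Complications are plausibly tied to troponin release, and major bleeding is itself an endpoint component.

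At stake is how Table 15(a) is read. It has the same format as Table 15 and could appear to contradict a valid unadjusted result.

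**Working it through.** **Plan's own figures.** With a 51% event rate in both arms, margin 0.191 and one-sided alpha 0.025, n per arm = (1.960 + z)² × 2 × 0.51 × 0.49 / 0.191².
- 99% power (z = 2.326): 251.7, so 504 in total (plan: about 500).
- 94.5% power (z = 1.598): 173.5, so 348 in total (plan: about 350).

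**Inputs for the check.** From the documents: durations as above, a 45-minute average procedure (Protocol 1.4.4; common to the arms, so it cancels), 51% event rate, about 500 and 350 patients. Assumed, because the documents do not say: post-PCI infusion uniform over 1-2 h (short) and either uniform over 12-18 h or all 18 h (comparator); departures in 0, 2, 5 or 10% of an arm; extended short infusions uniform over 12-18 h; early stops uniform over 0.5-12 h. Differences are short minus comparator, so positive means short is worse.

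**Collinearity, no departures, comparator 12-18 h.** Mean gap 15 − 1.5 = 13.5 h. Between-arm variance (13.5/2)² = 45.56. Mean within-arm variance (1/12 + 3)/2 = 1.54. VIF = (45.56 + 1.54)/1.54 = 30.6, r = 0.98. If all comparator infusions last 18 h, the simulated VIF exceeds 1,000.

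**Precision, 250 per arm.** Unadjusted half-width = 1.96 × √(2 × 0.51 × 0.49/250) = 8.8 points. A linear approximation multiplies this by √VIF. The simulation fitted logistic models and standardised the risks. Departures are at the stated rate in each arm and unrelated to outcome.

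| Departures | VIF | 8.76 × √VIF | Simulated half-width |
|---|---|---|---|
| 0% | 30.7 | 48.5 | 43.6 |
| 2% | 11.0 | 29.1 | 27.4 |
| 5% | 5.7 | 20.9 | 20.4 |
| 10% | 3.2 | 15.7 | 15.5 |

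For short versus long tirofiban, 10.5 points unadjusted (175 per arm) becomes 49.9, 32.2, 24.0 and 18.4. At 250/100, 11.6 becomes 58.3, 33.3, 24.3 and 18.6. That split solves pairwise totals of 500, 350 and 350 but sums to 600, against the stated approximately 550, so it is an assumption. Long tirofiban versus eptifibatide shows no collinearity (VIF 1.0).

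**Bias, true difference 0.** Approximately, adjusted difference = 0 − b × (mean short hours − mean comparator hours), where b is the pooled within-arm slope of risk on hours. Take 5% departures, odds ratio 3 and 51% overall in each arm. Risk is then 0.4975 without and 0.7481 with a departure, a difference of 0.2506.
- Short-arm extensions only, comparator 12-18 h: covariance 0.05 × 0.95 × 13.5 × 0.2506 = 0.1607; variances 8.886 (short) and 3 (comparator); b = 0.1607/11.886 = 0.01352; mean gap 2.175 − 15 = −12.825. Bias +17.3 points (simulated +16.8 to +17.6).
- The same with comparator at 18 h: b = 0.1607/8.886 = 0.01809; gap −15.825. Bias +28.6 (simulated about +27 to +28.5).
- Comparator early stops only, 12-18 h: covariance 0.0475 × (6.25 − 15) × 0.2506 = −0.1042; variances 7.038 and 0.083; b = −0.01463; gap 1.5 − 14.5625 = −13.0625. Bias −19.1 (simulated −18.4). At 18 h, simulated about −29.
- Both kinds, 12-18 h: b = (0.1607 − 0.1042)/(8.886 + 7.038) = 0.00355; gap −12.3875. Bias +4.4.

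Over 2-10% departures in one arm at odds ratio 3, the simulated bias runs from about 12 to 29 points either way. At odds ratio 2 and 12-18 h it is +9.2 to +12.4 (extensions) or −8.4 to −14.9 (stops). With both kinds at odds ratio 3 it is +2 to +5, rising to +7 to +9 if comparator complications also lengthen infusions to 18-24 h.

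**Chance of entry, outcome screen, 250 per arm.** Equal rates and unrelated departures: 4-5% at p<0.05, 17-21% at p<0.20. One-arm departures linked at odds ratio 3: 5-17% and 21-41%. True difference of 10 points: 52-61% and 76-84%. A screen on difference between arms would always admit it.

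**Vessel flag.** SAP 2.7.1 admits PCI without a stent. Coding one or more stents as multivessel therefore separates stented from unstented patients, and a patient with one stent in one vessel is called multivessel. Reading the threshold as more than one stent would not repair it, since two stents can lie in one vessel.

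**The case against.** The strongest reply is that no decision rests on this. The model is labelled exploratory, the non-inferiority claim uses the treatment-only model, and SAP 3.11 ties any claim to the primary endpoint. That stands. A reader might infer that the primary result is threatened; SAP 3.10.1 shows that it is not. A reader might also infer that infusion time will be in the model. The SAP only considers it, and under the design assumption of equal rates an outcome screen at p<0.05 would admit it about 5% of the time. What remains is that no criterion or threshold is stated, nothing excludes post-randomisation variables, and entry becomes likely when the arms differ, which is when the table will be read most closely.

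Second, the bias figures are driven by assumption, in sign and size. This also stands. Departure rates, their link to outcome and the spread of comparator infusions are not in the documents, so the figures are ranges and not predictions.

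Third, adjustment would not remove the whole contrast in short tirofiban versus eptifibatide, because the drug difference remains. That is correct, and the point is limited accordingly.

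Fourth, it is tempting to say that stent count, vessels treated and the P2Y12 timing windows must go too because they are fixed at or after randomisation. The documents do not make that case. The decision to proceed to PCI precedes randomisation, stents and vessels largely reflect anatomy, and Protocol 5.2.3 makes the last P2Y12 window largely a marker of earlier status. Removing them is a preference.

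**Conclusion.** The point holds for the exploratory adjusted model in the two short-tirofiban comparisons, conditional on entry. Total infusion time is a consequence of assignment. Including it costs precision (about 9 to roughly 16-44 points at 250 per arm, for 10% to 0% departures and comparators at 12-18 h). It can also shift the estimate by an amount comparable with the 19.1-point margin: about 12 to 29 points either way with one-arm departures of 2-10% at odds ratio 3, or about +2 to +9 when both kinds occur. In long tirofiban versus eptifibatide the variable is still post-randomisation, but collinearity does not arise. The confirmatory test stands as written.

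The Table 13 footnote is a definite error in a planned descriptive table. Its carry-over into the model is only possible: SAP 3.10.4 does not say how number of vessels treated is derived. Both should be corrected before analysis.

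**What to change.** 1. Delete total infusion time from the candidates for the between-arm adjusted models, including their interaction terms, in SAP 3.10.4 and the Table 15(a) note. Record that this departs from the list in Protocol 9.3.4. Nothing is lost, because mock Tables 2a and 2b already summarise hours of exposure by arm.
2. Replace Table 13 footnote 2: multivessel means two or more vessels treated, derived from recorded stent position (Protocol 5.2.3) and, for unstented lesions, from treated-vessel data if the CRF holds them. If it does not, drop the flag and report stent count only. In neither case use the present flag as the covariate for number of vessels treated.

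The cost is SAP wording and programming, with no new data. The documents do not state whether the CRF identifies vessels treated without a stent, so the flag may have to go.

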3.11 Multiplicity

The clinical decision rule is that tirofiban can only claim to have demonstrated an effect if it shows a clinical benefit based on the primary endpoint (death, PPM, uTVR or REPLACE-2 Major bleeding) within 48 hours following PCI or hospital discharge, whichever comes first), irrespective of the outcome of the secondary endpoints. No adjustments for multiple testing will be made.

3.12 Interim Analysis

No interim analyses will be conducted.

3.13 Accounting for Missing, Unused, and Spurious Data

Imputation methods will not be used for missing data.

5 HISTORICAL CHANGE

Version Number	Section(s) Changed	Reason(s) for change
1	N/A	New document
2	3.1.1 Analysis Conventions	Addition of further specifications with respect to the analysis conventions for rounding, decimal places, listing and table formatting, date imputation , and statistical software to be used.

Modified Intent-to-Treat Population (mITT) ¹ , n (%) *				
Per-Protocol Population (PP) ² , n (%) *				
Safety Population I ³ , n (%)				
Completed the study, n (%) *				
Yes				
No				
If no, reason for non-completion of the study, n (%) †				
Non-compliance with study protocol				
Adverse event				
Death				
Withdrawal of consent				
Treating physician decision to withdraw subject				
Other reason				

¹ Defined as all randomized patients who underwent PCI and received study drug.

² Defined as all randomized patients who completed the full course of the study without major protocol violations.

³ Defined as all randomized patients who received any study treatment.

* Percentages based on the total number of mITT patients in each treatment group.

† Percentages based on the total number of mITT patients who had a premature study discontinuation.

Table 2a. Treatment Exposure and Dosing by Treatment Group – mITT Population without renal insufficiency¹

Parameter	Treatment Group		
	Short Tirofiban (N=)	Eptifibatide (N=)	Long Tirofiban (N=)
Number of hours exposed to treatment drug			
Available n			
Mean ± SD			
95% CI for Mean			
Median (IQR)			
Min - Max			
Cumulative treatment drug received (µg)			
Available n			
Mean ± SD			
95% CI for Mean			
Median (IQR)			
Min - Max			

¹ Creatinine clearance >60 mL/min

Note: This table will also be repeated for Per-Protocol Population.

Table 2b. Treatment Exposure and Dosing by Treatment Group – mITT Population with renal insufficiency¹

Parameter	Treatment Group		
	Short Tirofiban (N=)	Eptifibatide (N=)	Long Tirofiban (N=)
Number of hours exposed to treatment drug			
Available n			
Mean ± SD			
95% CI for Mean			
Median (IQR)			
Min - Max			
Cumulative treatment drug received (µg)			
Available n			
Mean ± SD			
95% CI for Mean			
Median (IQR)			
Min - Max			

¹ Creatinine clearance ≤60 mL/min

Note: This table will also be repeated for Per-Protocol Population.

Table 3. Patient Demographics and Baseline Characteristics by Treatment Group – mITT Population

Parameter	Treatment Group		
	Short Tirofiban (N=)	Short Tirofiban (N=)	Short Tirofiban (N=)
Age (years)			
Available n			
Mean ± SD			
95% CI for Mean			
Median (IQR)			
Min - Max			
Gender, n (%)			
Female			
Male			
Ethnicity, n (%)			
Latino			
Non-Latino			
Race, n (%)			
White			
Black or African American			
Asian			
Native Hawaiian or other Pacific Islander			
American Indian or Alaska Native			
Other			

Note: This table will also be repeated for Per-Protocol Population.

Table 4. Concomitant Medications by Treatment Group– mITT Population

Medication	Treatment Group		
	Short Tirofiban (N=)	Short Tirofiban (N=)	Short Tirofiban (N=)
Aspirin, n (%)			
Yes			
No			
Oral P2Y12 antagonist -Clopidogrel, n (%)			
Yes			
No			
Oral P2Y12 antagonist - Prasugrel n (%)			
Yes			
No			
Oral P2Y12 antagonist- Ticagrelor, n (%)			
Yes			
No			
I.V. Heparin, n (%)			
Yes			
No			
Oral, sublingual, topical, or I.V. nitrates, n (%)			
Yes			
No			
Calcium channel blockers n (%)			
Yes			
No			

Medication	Treatment Group		
	Short Tirofiban (N=)	Short Tirofiban (N=)	Short Tirofiban (N=)
Lipid-lowering therapy n (%)			
Yes			
No			
Ace-inhibitors n (%)			
Yes			
No			
Beta-blocker n (%)			
Yes			
No			
Nonsteroidal anti-inflammatory agents n (%)			
Yes			
No			
Other cardioactive medications n (%)			
Yes			
No			
Angiotensin Receptor Blockers n (%)			
Yes			
No			
Diuretics n (%)			
Yes			
No			
Insulin n (%)			

RESPONSIVE
RELIABLE
RESULTS

SAVI-PCI
Statistical Analysis Plan
Version FINAL
20 February, 2019
Page 45 of 79

Medication	Treatment Group		
	Short Tirofiban (N=)	Short Tirofiban (N=)	Short Tirofiban (N=)
Yes			
No			

Note: This table will also be repeated for Per-Protocol Population.

Table 5. Concomitant Antiplatelet/Anticoagulant Dose by Treatment Group – mITT Population

Parameter	Treatment Group		
	Short Tirofiban (N=)	Eptifibatide (N=)	Long Tirofiban (N=)
Aspirin (mg)			
Available n			
Mean ± SD			
95% CI for Mean			
Median (IQR)			
Min - Max			
Oral P2Y12 antagonist loading dose- Clopidogrel (mg)			
Available n			
Mean ± SD			
95% CI for Mean			
Median (IQR)			
Min - Max			
Oral P2Y12 antagonist maintenance dose- Clopidogrel (mg)			
Available n			
Mean ± SD			
95% CI for Mean			
Median (IQR)			
Min - Max			
Oral P2Y12 antagonist loading dose- Prasugrel (mg)			
Available n			
Mean ± SD			

Parameter	Treatment Group		
	Short Tirofiban (N=)	Eptifibatide (N=)	Long Tirofiban (N=)
95% CI for Mean			
Median (IQR)			
Min - Max			
Oral P2Y12 antagonist maintenance dose- Prasugrel (mg)			
Available n			
Mean \pm SD			
95% CI for Mean			
Median (IQR)			
Min - Max			
Oral P2Y12 antagonist loading dose- Ticagrelor (mg)			
Available n			
Mean \pm SD			
95% CI for Mean			
Median (IQR)			
Min - Max			
Oral P2Y12 antagonist maintenance dose- Ticagrelor (mg)			
Available n			
Mean \pm SD			
95% CI for Mean			
Median (IQR)			
Min - Max			
IV Heparin (IU)			

RESPONSIVE
RELIABLE
RESULTS

SAVI-PCI
Statistical Analysis Plan
Version FINAL
20 February, 2019
Page 48 of 79

Parameter	Treatment Group		
	Short Tirofiban (N=)	Eptifibatide (N=)	Long Tirofiban (N=)
Available n			
Mean \pm SD			
95% CI for Mean			
Median (IQR)			
Min - Max			

Note: This table will also be repeated for Per-Protocol Population.

Table 6. Medical History by Treatment Group – mITT Population

System Organ Class (SOC) Preferred Term (PT)	Short Tirofiban (N=)		Eptifibatide (N=)		Long Tirofiban (N=)	
	Event	Subject (%)	Event	Subject (%)	Event	Subject (%)
TOTAL (ALL SOC/PT)						
SOC 1						
PT 1.1						
PT 1.2						
SOC 2						
PT 2.1						
PT 2.2						

Note: Medical history were coded by MedDRA version x. A patient may have reported more than one medical history. Percentages based on the total number of mITT patients in treatment group.

NA= Not Applicable

Note: This table will also be repeated for Per-Protocol Population.

Table 7(a). Vital Signs Prior to Randomization by Treatment Group – mITT Population

Vital Signs	Treatment Group		
	Short Tirofiban (N=)	Eptifibatide (N=)	Long Tirofiban (N=)
Height (cm)			
Available n			
Mean ± SD			
95% CI for Mean			
Median (IQR)			
Min - Max			
Weight (kg)			
Available n			
Mean ± SD			
95% CI for Mean			
Median (IQR)			
Min - Max			
Body temperature (°C)			
Available n			
Mean ± SD			
95% CI for Mean			
Median (IQR)			
Min - Max			
Heart rate (beats/minute)			
Available n			
Mean ± SD			

RESPONSIVE
RELIABLE
RESULTS

SAVI-PCI
Statistical Analysis Plan
Version FINAL
20 February, 2019
Page 51 of 79

Vital Signs	Treatment Group		
	Short Tirofiban (N=)	Eptifibatide (N=)	Long Tirofiban (N=)
95% CI for Mean			
Median (IQR)			
Min - Max			
Systolic blood pressure (mmHg)			
Available n			
Mean \pm SD			
95% CI for Mean			
Median (IQR)			
Min - Max			
Diastolic blood pressure (mmHg)			
Available n			
Mean \pm SD			
95% CI for Mean			
Median (IQR)			
Min - Max			

Note: This table will also be repeated for Per-Protocol Population.

Table 7(b). Vital Signs at 9±3 Hours following PCI by Treatment Group – mITT Population

Vital Signs	Treatment Group		
	Short Tirofiban (N=)	Eptifibatide (N=)	Long Tirofiban (N=)
Heart rate (beats/minute)			
Available n			
Mean ± SD			
95% CI for Mean			
Median (IQR)			
Min - Max			
Systolic blood pressure (mmHg)			
Available n			
Mean ± SD			
95% CI for Mean			
Median (IQR)			
Min - Max			
Diastolic blood pressure (mmHg)			
Available n			
Mean ± SD			
95% CI for Mean			
Median (IQR)			
Min - Max			

Note: This table will also be repeated for Per-Protocol Population.

Table 8. Physical Examination Prior to Randomization by Treatment Group – mITT Population

Body System	Treatment Group		
	Short Tirofiban (N=)	Eptifibatide (N=)	Long Tirofiban (N=)
Cardiovascular, n (%)			
Normal			
Abnormal			
Dermatological, n (%)			
Normal			
Abnormal			
Endocrine, n (%)			
Normal			
Abnormal			
Gastrointestinal, n (%)			
Normal			
Abnormal			
Genitourinary, n (%)			
Normal			
Abnormal			
H/E/N/T, n (%)			
Normal			
Abnormal			
Hematological, n (%)			
Normal			
Abnormal			

RESPONSIVE
RELIABLE
RESULTS

SAVI-PCI
Statistical Analysis Plan
Version FINAL
20 February, 2019
Page 54 of 79

Body System	Treatment Group		
	Short Tirofiban (N=)	Eptifibatide (N=)	Long Tirofiban (N=)
Hepatobiliary, n (%)			
Normal			
Abnormal			
Immunological, n (%)			
Normal			
Abnormal			
Lymphatic, n (%)			
Normal			
Abnormal			
Musculoskeletal, n (%)			
Normal			
Abnormal			
Nervous, n (%)			
Normal			
Abnormal			
Renal, n (%)			
Normal			
Abnormal			
Reproductive, n (%)			
Normal			
Abnormal			
Respiratory, n (%)			

RESPONSIVE
RELIABLE
RESULTS

SAVI-PCI
Statistical Analysis Plan
Version FINAL
20 February, 2019
Page 55 of 79

Body System	Treatment Group		
	Short Tirofiban (N=)	Eptifibatide (N=)	Long Tirofiban (N=)
Normal			
Abnormal			
Other, n (%)			
Normal			
Abnormal			

Note: This table will also be repeated for Per-Protocol Population.

Table 9. Serum Creatinine Results Prior to Randomization by Treatment Group – mITT Population

Tests	Treatment Group		
	Short Tirofiban (N=)	Eptifibatide (N=)	Long Tirofiban (N=)
Serum creatinine (mg/dL)			
Available n			
Mean ± SD			
95% CI for Mean			
Median (IQR)			
Min - Max			
Creatine clearance (ml/min) ¹			
Available n			
Mean ± SD			
95% CI for Mean			
Median (IQR)			
Min - Max			
Serum creatinine, n (%)			
Clinically significant			
Non-clinically significant			

¹ Cockcroft and Gault formula

Note: This table will also be repeated for Per-Protocol Population.

Table 10. Hematology Lab Results at Each Visit by Treatment Group – mITT Population

Tests	Treatment Group		
	Short Tirofiban (N=)	Eptifibatide (N=)	Long Tirofiban (N=)
Hemoglobin (g/dL)			
Available n			
Mean ± SD			
95% CI for Mean			
Median (IQR)			
Min - Max			
Hemoglobin, n (%)			
Clinically significant			
Non-clinically significant			
Hematocrit (%)			
Available n			
Mean ± SD			
95% CI for Mean			
Median (IQR)			
Min - Max			
Hematocrit, n (%)			
Clinically significant			
Non-clinically significant			
Platelet count, 10 ⁹ /L			
Available n			
Mean ± SD			

Tests	Treatment Group		
	Short Tirofiban (N=)	Eptifibatide (N=)	Long Tirofiban (N=)
95% CI for Mean			
Median (IQR)			
Min - Max			
Platelets, n (%)			
Clinically significant			
Non-clinically significant			

Note: This table will also be repeated for the Per-Protocol Population and for each of the following timepoints:

- *Prior to Randomization*
- *Prior to PCI*
- *9±3 h following PCI*
- *21±3 h following PCI*
- *42±6 h following PCI*

Table 11. Troponin Results at Each Visit by Treatment Group – mITT Population

Tests	Treatment Group		
	Short Tirofiban (N=)	Eptifibatide (N=)	Long Tirofiban (N=)
Troponin (µg/L)			
Available n			
Mean ± SD			
95% CI for Mean			
Median (IQR)			
Min - Max			
Troponin, n (%)			
Clinically significant			
Non-clinically significant			

Note: This table will be repeated for the Per-Protocol Population and for each of the following timepoints:

- *Prior to PCI*
- *9±3 h following PCI*
- *21±3 h following PCI*
- *42±6 h following PCI*

Table 12. Descriptive Statistics of Bleeding Sites and Treatment of Bleed by Treatment Group – mITT Population

Parameter	Treatment Group		
	Short Tirofiban (N=)	Short Tirofiban (N=)	Short Tirofiban (N=)
Bleeding Site, n (%)			
Intracranial			
Retroperitoneal			
Sheath puncture site			
Other puncture site			
ENT bleed			
GI bleed			
GU bleed			
Cardio/pulmonary bleed			
Other			
Treatment of Bleed, n (%)			
Transfusion			
Pressure Dressing			
No treatment			
If transfusion, type of transfusion, n (%)			
Heparinized pump blood replacement			
Whole blood			
PRBCs			
FFP			
Platelets			
Cryoprecipitate			

RESPONSIVE
RELIABLE
RESULTS

SAVI-PCI
Statistical Analysis Plan
Version FINAL
20 February, 2019
Page 61 of 79

Parameter	Treatment Group		
	Short Tirofiban (N=)	Short Tirofiban (N=)	Short Tirofiban (N=)
Cell-saver			
Albumin			
Other			

Note: This table will also be repeated for Per-Protocol Population

Table 13. Descriptive Statistics of Potential Covariates Not Summarized Elsewhere by Treatment Group – mITT Population

Parameter	Treatment Group		
	Short Tirofiban (N=)	Eptifibatide (N=)	Long Tirofiban (N=)
Age category, years, n (%)			
< 65			
≥ 65- 74			
≥ 75			
Patient with acute coronary syndromes ¹ , n (%)			
Yes			
No			
STEMI > 48 hours, n (%)			
Yes			
No			
Stable angina, n (%)			
Yes			
No			
Troponin baseline, n (%)			
Negative			
Positive			
Planned PCI access, n (%)			
Femoral			
Radial			
Number of stents implanted			

Parameter	Treatment Group		
	Short Tirofiban (N=)	Eptifibatide (N=)	Long Tirofiban (N=)
Available n			
Mean ± SD			
95% CI for Mean			
Median (IQR)			
Min - Max			
Vessel involvement, n (%) ²			
Single Vessel			
Multivessel			
Patients receiving P2Y12 antagonist therapy between 24 and 6 hours prior to randomization, n (%)			
Yes			
No			
Patients receiving P2Y12 antagonist therapy between 6 and 1 hours prior to randomization, n (%)			
Yes			
No			
Patients receiving P2Y12 antagonist therapy between 1 hour prior to randomization and 15 minutes after completion of the PCI procedure, n (%)			
Yes			
No			
Type 2 diabetes mellitus, n (%)			
Yes			
No			
Indication for PCI, n (%)			

Parameter	Treatment Group		
	Short Tirofiban (N=)	Eptifibatide (N=)	Long Tirofiban (N=)
Elective			
Urgent			

¹ Defined as any previous diagnosis of unstable angina, NSTEMI or STEMI

² Ascertained by 'Number if stents implanted' indicated on the Procedure Report Form; ≥ 1 implanted stent = multivessel

Note: This table will also be repeated for Per-Protocol Population.

Table 14. Descriptive Statistics of Primary Outcome by Treatment Group – mITT Population

Parameter	Treatment Group		
	Short Tirofiban (N=)	Eptifibatide (N=)	Long Tirofiban (N=)
Primary outcome, n (%)			
Yes			
No			
Death, n (%)			
Yes			
No			
Periprocedural myonecrosis (PPM), n (%)			
Yes			
No			
Urgent target vessel revascularization (uTVR), n (%)			
Yes			
No			
REPLACE-2 major bleeding, n (%)			
Yes			
No			

Note: The primary outcome is the composite of death, PPM, uTVR or REPLACE-2 major bleeding within 48 hours following PCI or hospital discharge, whichever comes first.

Note: This table will also be repeated for Per-Protocol Population.

Table 15. Bivariate Logistic Regression Model for Primary Outcome – mITT Population

Parameter	Level	Estimate	Standard Error (SE)	Odds Ratio (OR)	95% CI for OR	Risk (Proportion Difference)	Standard Error (SE) of Risk Difference	95% CI for Risk Difference	p-value *
Primary composite outcome	Short Tirofiban vs. Eptifibatide								
Primary composite outcome	Short Tirofiban vs. Long Tirofiban								
Primary composite outcome	Long Tirofiban vs. Eptifibatide								

* p-value is the overall p-value from the logistic regression model.

Note: The primary outcome is the composite of death, PPM, uTVR or REPLACE-2 major bleeding within 48 hours following PCI or hospital discharge, whichever comes first.

Note: This table will also be repeated for Per-Protocol Population.

Table 15 (a) Multivariate Logistic Regression Models for Primary Outcome – mITT Population

Parameter	Level	Estimate	Standard Error (SE)	Odds Ratio (OR)	95% CI for OR	Risk (Proportion Difference)	Standard Error (SE) of Risk Difference	95% CI for Risk Difference	p-value *
Primary composite outcome	Short Tirofiban vs. Eptifibatide								
Primary composite outcome	Short Tirofiban vs. Long Tirofiban								
Primary composite outcome	Long Tirofiban vs. Eptifibatide								

* p-value is the overall p-value from the logistic regression model.

Note: The following potential covariates, as well as all significant 2-way interaction terms, will be assessed using appropriate univariate statistics for consideration in the multivariate regression models:

- *Patient with acute coronary syndrome*
- *STEMI > 48 hours*
- *Stable angina*
- *Baseline troponin (positive vs. negative)*
- *Planned PCI access (femoral vs. radial)*
- *Number of stents implanted*
- *Number of vessels treated (multivessel vs. single vessel)*
- *Total infusion time*
- *Patients receiving P2Y12 antagonist therapy between 24 and 6 hours prior to randomization*
- *Patients receiving P2Y12 antagonist therapy between 6 and 1 hours prior to randomization*
- *Patients receiving P2Y12 antagonist therapy between 1 hour prior to randomization and 15 minutes after completion of the PCI procedure*
- *Type 2 diabetes mellitus*
- *Age < 65 years, ≥ 65- 74 years and ≥ 75 years*

- *Sex*
- *Clopidogrel*
- *Prasugrel*
- *Ticagrelor*
- *Indication for PCI (Urgent vs. Elective)*

Note: This table will also be repeated for Per-Protocol Population.

Table 16. Descriptive Statistics of Secondary Outcomes by Treatment Group – mITT Population

Parameter	Treatment Group		
	Short Tirofiban (N=)	Short Tirofiban (N=)	Short Tirofiban (N=)
Secondary outcome 1, n (%)			
Yes			
No			
Secondary outcome 2, n (%)			
Yes			
No			
Secondary outcome 3, n (%)			
Yes			
No			
Secondary outcome 4, n (%)			
Yes			
No			
Secondary outcome 5, n (%)			
Yes			
No			
Secondary outcome 6, n (%)			
Yes			
No			
Secondary outcome 7, n (%)			
Yes			
No			

Parameter	Treatment Group		
	Short Tirofiban (N=)	Short Tirofiban (N=)	Short Tirofiban (N=)
Secondary outcome 8, n (%)			
Yes			
No			

Note: The definitions of secondary outcomes are:

- *Secondary outcome 1: death, PPM or uTVR within 48 hours following PCI or hospital discharge, whichever comes first*
- *Secondary outcome 2: PPM within 48 hours following PCI or hospital discharge, whichever comes first*
- *Secondary outcome 3: uTVR within 48 hours following PCI or hospital discharge, whichever comes first*
- *Secondary outcome 4: death within 48 hours following PCI or hospital discharge, whichever comes first*
- *Secondary outcome 5: death, PPM, uTVR or major bleeding within 48 hours following PCI or hospital discharge, whichever comes first, where PPM is defined as at least one troponin elevation of ≥ 10 times the upper limit of normal and at least 20% of greater than the baseline troponin value, per the troponin Local Laboratory within 48 hours following PCI or hospital discharge, whichever comes first (a non-inferiority margin of 12.4% will be used for the short tirofiban versus eptifibatide comparison)*
- *Secondary outcome 6: at least one troponin elevation of ≥ 10 times the upper limit of normal and at least 20% of greater than the baseline troponin value, per the troponin Local Laboratory, within 48 hours following PCI or hospital discharge, whichever comes first (a noninferiority margin of 12.4% will be used for the short tirofiban versus eptifibatide comparison)*
- *Secondary outcome 7: at least one troponin elevation of ≥ 20 times the upper limit of normal and at least 20% of greater than the baseline troponin value, per the troponin Local Laboratory, within 48 hours following PCI or hospital discharge, whichever comes first*
- *Secondary outcome 8: at least one troponin elevation of ≥ 50 times the upper limit of normal and at least 20% of greater than the baseline troponin value, per the troponin Local Laboratory, within 48 hours following PCI or hospital discharge, whichever comes first*

Note: This table will also be repeated for Per-Protocol Population.

Table 17. Bivariate Logistic Regression Model for Secondary Outcomes – mITT Population

Parameter	Level	Estimate	Standard Error (SE)	Odds Ratio (OR)	95% CI for OR	Risk (Proportion Difference)	Standard Error (SE) of Risk Difference	95% CI for Risk Difference	p-value *
Secondary outcome	Short Tirofiban vs. Eptifibatide								
Secondary outcome	Short Tirofiban vs. Long Tirofiban								
Secondary outcome	Long Tirofiban vs. Eptifibatide								

* p-value is the overall p-value from the logistic regression model.

Note: The definitions of secondary outcomes are:

- *Secondary outcome 1: death, PPM or uTVR within 48 hours following PCI or hospital discharge, whichever comes first*
